6.1. Adverse Events

The Medical Dictionary for Regulatory Activities (MedDRA) (version 18.1 or above) will be used to classify AEs by system organ class and preferred term. TEAEs that occurred in each study phase will be summarized by system organ class and preferred term.

The number (%) of subjects with TEAEs, serious TEAEs (SAEs), and TEAEs that led to study drug discontinuation will be summarized by system organ class and preferred term. Data listings will be generated for deaths, other SAEs, and discontinuations due to AEs.

In addition, data listing and summary will be provided for subjects with AEs ongoing at the time of entry into this study.

A TEAE is an event that is new in onset or increased in severity following treatment initiation. An event that starts prior to, and ends after the initiation of study medication will be considered treatment-emergent only if the severity increases after the start of medication.

Treatment-emergent adverse events (TEAEs) are defined as follows for each study phase:

- TEAEs in the induction phase:
 - a. If AE onset time is not missing:
 - i) If subjects continue to OP/MA phase: IND phase start date/time \leq AE onset date and time $<$ IND phase end date
 - ii) If subjects discontinue in the IND phase: IND phase start date/time \leq AE onset date and time \leq IND phase end date

-
- b. If AE onset time is missing:
 - i) If subjects continue to OP/MA phase: IND phase start date/time \leq AE onset date $<$ IND phase end date
 - ii) If subjects discontinue in the IND phase: IND phase start date/time \leq AE onset date \leq IND phase end date
 - TEAEs in the optimization/maintenance phase:
 - a. If AE onset time is not missing: OP/MA phase start date/time \leq AE onset date and time \leq OP/MA phase end date
 - b. If AE onset time is missing: OP/MA phase start date \leq AE onset date \leq OP/MA phase end date
 - For the AEs that have both day and month missing, treatment-emergent flag is assigned based on the rules presented in Section 2.6.

In addition, TEAEs will be summarized by severity and relationship to study medication using the preferred term. For the summaries of TEAEs by severity/relationship to study medication, the observation with the most severe occurrence/closest relationship to study medication will be chosen if there is more than one incident of an AE reported during the analysis phase by the subject. AE duration for transient dizziness/vertigo and anxiety will also be summarized.

Adverse Events of Special Interest

Clinically relevant TEAEs of special interest will be examined separately grouped in the following categories:

- drug abuse, dependence and withdrawal (Aggression, Confusional state, Decreased activity, Dependence, Disorientation, Dissociation, Dissociative disorder, Dizziness, Drug use disorder, Drug abuse, Drug abuser, Drug dependence, Drug detoxification, Drug diversion, Drug rehabilitation, Drug tolerance, Drug tolerance increased, Drug withdrawal convulsions, Drug withdrawal headache, Drug withdrawal syndrome, Euphoric mood, Feeling abnormal, Feeling drunk, Feeling of relaxation, Hallucination, Hallucination auditory, Hallucination gustatory, Hallucination olfactory, Hallucination synaesthetic, Hallucination tactile, Hallucination visual, Hallucinations mixed, Inappropriate affect, Mental impairment, Product tampering, Psychomotor hyperactivity, Psychotic disorder, Rebound effect, Somatic Hallucination, Somnolence, Substance abuser, Substance dependence, Substance use, Substance use disorder, Substance-induced mood disorder, Substance-induced psychotic disorder, Thinking abnormal, Withdrawal arrhythmia, Withdrawal syndrome);
- increased blood pressure (Blood pressure increased, Blood pressure diastolic increased, Blood pressure systolic increased, Hypertensive crisis, Hypertensive emergency, Hypertension);
- increased heart rate (Heart rate increased, Tachycardia, Extrasystoles);
- transient dizziness/vertigo (Dizziness, Dizziness exertional, Dizziness postural, Procedural dizziness, Vertigo, Vertigo labyrinthine, Vertigo positional, Vertigo CNS origin);
- impaired cognition (Cognitive disorder);

-
- cystitis (Allergic cystitis, Chemical cystitis, Cystitis, Cystitis erosive, Cystitis haemorrhagic, Cystitis interstitial, Cystitis noninfective, Cystitis ulcerative, Cystitis-like symptom, Pollakiuria, Dysuria, Micturition urgency, Nocturia);
 - anxiety (Anticipatory anxiety, Anxiety, Anxiety disorder, Agitation, Fear, Feeling jittery, Irritability, Nervousness, Panic attack, Tension);
 - events potentially related to suicidality (Completed suicide, Depression suicidal, Intentional overdose, Intentional self-injury, Multiple drug overdose intentional, Poisoning deliberate, Self-injurious behavior, Self-injurious ideation, Suicidal behavior, Suicidal ideation, Suicide attempt)
 - hepatic adverse events (Cholecystitis, Cholelithiasis, Hepatic steatosis, Hepatitis, Non-alcoholic steatohepatitis, Primary biliary cholangitis, Alanine aminotransferase increased, Aspartate aminotransferase increased, Blood bilirubin increased, Gamma-glutamyl transferase increased, Hepatic enzyme increased, Liver function test abnormal, Liver function test increased, Transaminases increased, Urine bilirubin increased, Urobilinogen urine increased)
 - events related to renal disorders (Cystitis, Pyelonephritis, Urethritis, Urinary tract infection, Blood creatinine increased, Blood urea increased, Blood urine present, Creatinine renal clearance increased, Protein urine present, Urine analysis abnormal, Urine leukocyte esterase positive, Bladder discomfort, Bladder irritation, Bladder outlet obstruction, Cystitis noninfective, Dysuria, Haematuria, Hypertonic bladder, Lower urinary tract symptoms, Micturition urgency, Nephrolithiasis, Nocturia, Pollakiuria, Polyuria, Proteinuria, Renal colic, Renal failure, Semenuria, Stress urinary incontinence, Ureterolithiasis, Urge incontinence, Urinary bladder polyp, Urinary hesitation, Urinary incontinence, Urinary retention)
 - symptoms of dissociation persisting beyond the typical ≤ 2 hour post esketamine administration (dissociation)
 - delirium (Post-injection delirium sedation syndrome, Postoperative delirium, Delirium, Intensive care unit delirium)
 - psychosis (Acute psychosis, Affective disorder, Alcoholic psychosis, Bipolar I disorder, Epileptic psychosis, Hysterical psychosis, Mania, Parkinson's disease psychosis, Postictal psychosis, Psychosis postoperative, Psychotic disorder, Psychotic disorder due to a general medical condition, Reactive psychosis, Rebound psychosis, Schizoaffective disorder, Substance-induced psychotic disorder, Transient psychosis)
 - mania (Hypomania, Mania)

The number and percentage of subjects taking concomitant medication for dissociation events (preferred term of Dissociation) at any time during each treatment phase will be provided.

Summary statistics for the duration of all episodes of TEAEs associated with discharge readiness (Dissociation, Dizziness, Feeling abnormal, Feeling drunk, Nausea, Somnolence, Vertigo, and Vomiting) with an onset on the day of intranasal study drug administration will be provided for each treatment phase. During the induction phase the summaries are presented for each dosing session and during the optimization/maintenance phase the summaries are presented for the first four dosing sessions and at the Month 3, Month 6 and Month 9 dosing sessions. In addition, the number of occurrences of TEAEs associated with discharge readiness and the number of

occurrences of TEAEs associated with substance dependence is presented by dosing sessions for each treatment phase.

AEs collected at Follow-up phase for France subjects will be provided in a listing.

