	Subject was in the induction phase and did not meet criteria for response and sponsor has approved subject's entry into 54135419TRD3008	Induction phase or Optimization/maintenance phase
ESKETINTRD3005	Subject was in the induction phase of ESKETINTRD3005 study at the time enrollment into the ESKETINTRD3004 study was closed and, after completion of the induction phase, was determined to be a non-responder.	Induction phase
	Subject was in the induction phase of ESKETINTRD3005 study at the time enrollment into the ESKETINTRD3004 study was closed and, after completion of the induction phase, was determined to be a responder	Optimization/maintenance phase
ESKETINTRD3006 United States study sites only	Subject completed the induction phase and was a responder	Optimization/maintenance phase
	Subject completed induction phase and did not meet the response criteria, and sponsor has approved subject's entry into 54135419TRD3008	Induction phase or Optimization/maintenance phase

An Independent Data Monitoring Committee (IDMC) will meet approximately every 6 months to review select safety data through the end of 2020 (see Section 11.7, Independent Data Monitoring Committee, for details).

This study will have 2 open label phases

- A 4-week induction phase (if applicable, per Table 1 above)
- A variable duration optimization/maintenance phase

The duration that a subject may participate in the study is variable and is based on the subject's point of entry into the study and the timing of when the predefined criteria (below) for ending study participation occurs.

Study participation will be stopped:

- when esketamine is approved in the respective country and accessible through the local healthcare system funding or until end of December 2022, whichever is earlier; or
- the subject no longer benefits from further treatment (based on the investigator's clinical judgment), or withdraws consent; or
- the company terminates clinical development of esketamine nasal spray for TRD in that country/region

Subjects will have a final study visit within 1 week of the last dose of esketamine nasal spray.

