11.3. Safety Analyses

Safety data for the induction phase and the optimization/maintenance phase will be presented separately for each phase as well as for the entire treatment period (induction and optimization/maintenance phase). The baseline for safety assessments will be defined in the Statistical Analysis Plan.

Cognitive Function

Computerized cognitive test battery and HVLT-R: Descriptive statistics of each of the cognitive domain scores and changes from baseline will be provided at each scheduled time point.

Adverse Events

The verbatim terms used in the CRF by investigators to identify adverse events will be coded using the Medical Dictionary for Regulatory Activities (MedDRA). Treatment-emergent adverse events are adverse events with onset during the treatment phase or that are a consequence of a pre-existing condition that has worsened since baseline. All reported adverse events with onset during the treatment phase (ie, TEAEs, and adverse events that have worsened since baseline) will be included in the analysis. For each adverse event, the percentage of subjects who experience at least 1 occurrence of the given event will be summarized.

Treatment emergent AEs of special interest will be examined separately grouped in the following categories: drug abuse, dependence and withdrawal, increased blood pressure, increased heart rate, transient dizziness/vertigo, impaired cognition, cystitis, anxiety, events potentially related to suicidality, hepatic adverse events, events related to renal disorders, and symptoms of dissociation persisting beyond the typical ≤ 2 hour post esketamine administration, as well as delirium, psychosis or mania.

Summaries, listings, datasets, or subject narratives may be provided, as appropriate, for those subjects who die, who discontinue treatment due to an adverse event, or who experience a severe or a serious adverse event.

Vital Signs

Descriptive statistics of body weight, temperature, pulse/heart rate, respiratory rate, pulse oximetry and supine blood pressure (systolic and diastolic) values and changes from baseline will be provided at each scheduled time point. Any treatment-emergent abnormalities will be listed.

Clinical Laboratory Tests

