4.3. Extent of Exposure

Extent of exposure in terms of total duration of exposure and number of dosing sessions of intranasal study medication will be summarized by phase for the Full analysis sets and across both phases for the All Enrolled analysis set described in Section 2.4.2.

- The total duration of exposure for the intranasal study drug for each phase is defined as the time between the first and the last dose of study medication in that specific phase (last day of study medication - first day of study medication + 1). If a subject only receives a partial dose it is considered as a day of dosing.

Descriptive statistics (N, mean, SD, median, minimum and maximum) and frequency distribution of total duration of exposure of intranasal study drug will be presented. A frequency distribution of the total number of dosing sessions of intranasal study medication will be presented.

Starting at Week 4, during the optimization/maintenance phase, the number and percentage of subjects at each dosing frequency (weekly, every other week and every 4 weeks) and the number of subjects who changed their frequency will be summarized every 4 weeks.

- Modal dose for a subject is defined as the most frequently taken dose by a subject. Mean dose of a subject is calculated as the sum of doses during the phase divided by the total number of days exposed in the phase. The final dose is the last non-zero dose received during the phase. The calculation of mean, modal and final dose will exclude days off study drug.

Descriptive statistics (N, mean, SD, median, minimum and maximum) of modal dose, mean and final dose of intranasal study drug will be presented by phase. A frequency distribution of dose level (28, 56 and 84 mg) will be presented at each dosing session. In addition, at end of each phase the number and percentage of subjects at each dose (28, 56 and 84 mg) of intranasal study medication will be provided.

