6. SAFETY

Safety data for the induction and optimization/maintenance phases will be presented separately for each phase. Summaries for each phase will be based on the Full analysis sets described in Section 2.4.2. In addition, adverse event and cognition data will be summarized for the entire treatment period combining the induction and optimization/maintenance phases. Summaries for the entire treatment period will be based on the All Enrolled analysis set described in Section 2.4.1.

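### For the open-ended optimization/maintenance phase and the whole treatment period, adverse event incidence is planned only as a crude percentage of subjects, so it depends on length of stay

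*SAP*

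**What the plan says.** SAP 6.1: "The number (%) of subjects with TEAEs, serious TEAEs (SAEs), and TEAEs that led to study drug discontinuation will be summarized". The breakdown uses the MedDRA hierarchy. Protocol 11.3 agrees: for each event, "the percentage of subjects who experience at least 1 occurrence of the given event will be summarized". For events of special interest, SAP 6.1 lists preferred terms by category and names no statistic, so the percentage in Protocol 11.3 is the natural reading.

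These summaries are produced for each phase, and SAP 6 adds that "adverse event and cognition data will be summarized for the entire treatment period combining the induction and optimization/maintenance phases". Protocol 3.1: "The duration that a subject may participate in the study is variable". A subject leaves on local approval and funded access or at the end of December 2022 (whichever is earlier), on withdrawing consent, when development stops, or when "the subject no longer benefits from further treatment".

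Exposure is summarized separately in SAP 4.3. It "is defined as the time between the first and the last dose of study medication in that specific phase" and is not used as a denominator for adverse events.

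Two adverse event outputs in SAP 6.1 are indexed by dosing session. One is the duration of discharge-readiness episodes, where in OP/MA "the summaries are presented for the first four dosing sessions and at the Month 3, Month 6 and Month 9 dosing sessions". The other is a count of occurrences for discharge-readiness events and for substance dependence: "occurrences of TEAEs associated with substance dependence is presented by dosing sessions for each treatment phase".

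**The concern.** Safety is the primary objective, and the study's particular contribution is long follow-up. A percentage of subjects ever affected has a clear meaning when everyone is observed for the same time, as in the planned 4-week induction phase. In OP/MA, follow-up may be short or run to several years, so the same percentage can come from a high risk over a short stay or a low risk over a long one. It also cannot show whether events become more or less frequent as follow-up lengthens, which is the question a long-term extension is run to answer.

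Cystitis is the clearest case. The stated reason for protocol Amendment 3 includes collecting long-term data on urinary symptoms, and Protocol 3.2.5 follows cystitis as an adverse event. Cognition, the other subject of that amendment, has a full analysis by timepoint in SAP Attachment 2. Cystitis has a list of preferred terms and no time dimension.

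**Working it through.** **1. What the planned outputs can show**

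| Output | Covers | First-event rate or interval incidence? |
|---|---|---|
| Number and % (SAP 6.1, Protocol 11.3) | TEAEs, serious TEAEs, discontinuations | No |
| Exposure (SAP 4.3) | All subjects | No. N × mean exposure gives approximate subject-years, but only to the last dose and not stopped at the first event |
| Occurrence counts by session (SAP 6.1) | Discharge-readiness and substance-dependence events | No. Counts of occurrences, not of subjects at risk |
| Episode duration by session (SAP 6.1) | Discharge-readiness events | No |

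None of the time-indexed outputs covers cystitis, serious events or discontinuations.

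**2. Longest possible stay.** From the original protocol (08 February 2016) to 31 December 2022 is 2,518 days; 2,518 / 365.25 = 6.89 years = T. This is an upper bound. Actual follow-up is not stated.

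**3. Constant risk, different stay.** The documents give no event rates, exit rates or sample size, so there is no planned figure to reproduce. Every rate below is an assumption, and exit is taken as unrelated to risk. With first-event rate L, exit rate m = 1/(mean stay) and follow-up capped at T,

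crude proportion = L/(L+m) × [1 − exp(−(L+m)T)].

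Example, L = 0.05 and m = 0.5: 0.0909 × [1 − exp(−0.55 × 6.89)] = 0.0909 × 0.977 = 8.9%.

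| First events per 100 subject-years | Mean stay about 1 y | about 2 y | about 3 y |
|---|---|---|---|
| 2 | 2.0% | 3.7% | 5.2% |
| 5 | 4.8% | 8.9% | 12.1% |
| 10 | 9.1% | 16.4% | 21.9% |

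The cap shortens the nominal stays slightly: (1 − exp(−mT))/m is 1.00, 1.94 and 2.70 years. Within each row the rate is the same, and the percentage rises about 2.4- to 2.6-fold.

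**4. Opposite time patterns.** With yearly rates L1, L2, L3 over three years, exit rate m and S the proportion still at risk at the start of a year, each year contributes S × L/(L+m) × [1 − exp(−(L+m))].

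| Yearly rates per 100 | Exit per year | Contributions by year | Crude % |
|---|---|---|---|
| 2, 5, 8 (rising) | 0.20 | 1.80 + 3.55 + 4.36 | 9.7% |
| 8, 5, 2 (falling) | 0.20 | 6.98 + 3.34 + 1.06 | 11.4% |
| 8, 5, 2 (falling) | 0.374 | 6.43 + 2.59 + 0.69 | 9.7% |

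The 0.374 was chosen to produce the match. With equal exit the percentages still differ by under two points, while the yearly rates run in opposite directions.

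**5. Time origin for an OP/MA table.** Starting the clock at the first induction dose would put 4 of the first 26 weeks (15.4%) into the denominator when no OP/MA event can occur. At a true 5 per 100, events per subject are 1 − exp(−0.05 × 22/52) = 0.0209 and time is 4/52 + 0.0209/0.05 = 0.496 years, so the table would report 0.0209/0.496 = 4.22 per 100. A true 2 would appear as 1.69, and 10 as 8.43. The OP/MA table therefore needs its own origin.

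**6. Precision.** As an example, 10 first events in 500 subject-years is 2.0 per 100, exact 95% CI 0.96 to 3.68.

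**The case against.** The strongest reply is that nothing planned is wrong. The study is single-arm with no hypothesis (SAP 1.3), percentages are given by phase, and the exposure distribution is reported alongside. SAP 6.1 also plans listings of deaths, other serious events and discontinuations, SAP 2.1.3 defines the study day of an event, and the monitoring committee reviews these categories every six months (SAP 3; through the end of 2020 in Protocol 11.7). That limits the point to interpretation. But a listing is not an estimate, committee review runs in calendar time, and SAP 6.1 specifies no cystitis listing.

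A second reply is that urinalysis is summarized by visit (SAP 6.2) and includes blood and leukocyte esterase, and that Protocol 3.2.5 expects cystitis risk to be very low. Urinalysis helps, but most of the cystitis terms in SAP 6.1 are symptoms or diagnoses, such as dysuria, urgency and nocturia, which it does not count. The reply has more force for hepatic, renal and suicidality events, where laboratory values and C-SSRS are summarized by visit.

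Third, the illustration rests on assumed rates, and the longest stay is 2.70 years after the cap. With exit set so that the capped mean is exactly 3 years, the last column of the first illustration would be 5.7%, 13.4% and 24.0%. The direction does not change.

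Fourth, SAP 2.6 sets a completely missing onset date to the start of the subject's entry phase and pulls dates lacking day and month towards it. Used unchanged, this would push such events into the first interval. That is fair, and a footnote deals with it.

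**Conclusion.** The concern holds. For OP/MA and the entire treatment period, the planned incidence measure depends on how long subjects stay, and no planned output shows how the risk of serious events, discontinuations or cystitis changes over follow-up. Under the assumed constant rates, tripling the nominal mean stay from 1 to 3 years raises the percentage about two and a half times with no change in risk. The actual distortion cannot be sized because the documents give neither event rates nor realized follow-up. The induction table is largely unaffected, and no between-group comparison is at stake. This should be changed because it is cheap and serves the primary objective; it does not invalidate what is planned.

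**What to change.** Keep the percentages in SAP 6.1. For serious events, TEAEs leading to discontinuation and cystitis (hepatic, renal and suicidality optional), add:

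1. Subjects with a first event per 100 subject-years at risk, with 95% confidence interval.
2. First-event incidence by interval, for example 0–6, 6–12, 12–24, 24–36 and over 36 months, with numbers at risk.

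Time at risk:
- **OP/MA table:** from the OP/MA start date (SAP 2.1.2) to the first event in the category or the OP/MA end date.
- **Entire-period table:** from the reference start date (SAP 2.1.1) to the first event or the end of the last treatment phase, matching the treatment-emergent window in SAP 2.6.

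State whether subjects with an event in induction or ongoing at entry count as at risk in the OP/MA table, and footnote events whose onset date was imputed. Label intervals as time since entry to the phase or study, not total time on drug. Note that prior esketamine exposure differs by parent study (Protocol 9.1.3), that entrants are selected for favourable benefit-risk (Protocol 4.2), and that exit may be informative (Protocol 3.1).

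The cost is SAP wording and a few tables from dates already collected. Late intervals will be sparse with wide confidence intervals, and informative exit remains.

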Ketamine-induced ulcerative cystitis is a recently identified complication.⁴⁸ The most common symptoms are frequency and urgency of urination, dysuria, urge incontinence, and occasionally painful hematuria (blood in urine). Computerized tomography scans of these subjects revealed a marked thickening of the bladder wall, a small bladder capacity, and perivesicular stranding consistent with severe inflammation. At cystoscopy, all patients had severe ulcerative cystitis. Biopsies in 4 of these cases found denuded urothelial mucosa with thin layers of reactive and regenerating epithelial cells, and ulcerations with vascular granulation tissue and scattered inflammatory cells. Cessation of ketamine use provided some relief of symptoms. Most of the described cases are in near-daily users of ketamine for recreational purposes. The prevalence is difficult to determine, as it is seen in recreational users who often do not seek help.

The majority of cases resolve after stopping ketamine use, one-third remaining static.

Abuse Liability, Dependence, and Withdrawal

There are a number of reports of ketamine dependence in the literature^{31,33,46,54} but no large-scale studies, and so the incidence of ketamine dependence is largely unknown.⁴⁸ An interview study of 90 ketamine users found that 57% of frequent users, 43% of infrequent users, and 60% of ex-users expressed concerns about ketamine addiction.⁵¹ The majority of frequent users in that study reported using the drug without stopping until supplies ran out, so compulsive patterns of behavior are also a concern. Oral ketamine has also been evaluated as a positive control in human abuse potential studies, with dosages of 65 mg and 110 mg reported as appropriate for use as positive controls for future abuse potential studies of compounds with a similar mechanism of action or with possible perception-altering effects.⁶⁹ There is conflicting evidence of the existence of a "withdrawal syndrome" after cessation of ketamine use.⁴⁸ Cravings seem to be a key problem in

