3.2.5. Safety Evaluations

Evaluation of TEAEs and concomitant therapies, clinical laboratory tests, vital signs (including blood pressure measurements), 12-lead ECG, pulse oximetry, physical examination, and body weight, will be performed throughout the study as per the Time and Events Schedule to monitor subject safety.

Treatment emergent AEs of special interest will be analyzed separately grouped in the following categories: drug abuse, dependence and withdrawal (standardized Medical Dictionary for Regulatory Activities [MedDRA]), increased blood pressure, increased heart rate, transient dizziness/vertigo, impaired cognition, cystitis, anxiety, events potentially related to suicidality, hepatic adverse events, events related to renal disorders, and symptoms of dissociation persisting beyond the typical ≤ 2 hour post esketamine administration, as well as delirium, psychosis or mania.

The effect of esketamine nasal spray on cognition will be assessed as per the Time and Events Schedule using the computerized cognitive battery and Hopkins Verbal Learning Test-Revised (HVLT-R). The cognitive battery will provide assessment of multiple cognitive domains, including attention, visual learning and memory, and executive function. The HVLT-R is a measure of verbal learning and memory, and includes assessment of both immediate and delayed recall.

Even though it is anticipated that the potential risk for treatment-emergent cystitis is very low based upon the doses to be used in this study, subjects will be monitored for adverse events of cystitis, bladder pain, and interstitial cystitis during the study. If cystitis is considered to be associated with esketamine, subjects will be discontinued from the study and followed up with appropriate medical care.

Given the potential for treatment emergent transient elevation in systolic and diastolic blood pressure, heart rate and blood pressure will be monitored throughout the study and at multiple time points on dosing days. Specific guidance to be followed on intranasal dosing days is provided in Section 6.1.

The Columbia Suicide Severity Rating Scale (C-SSRS) will be performed as per the Time and Events Schedule to assess suicidal ideation and behavior, the MOAA/S will be used to measure treatment-emergent sedation, and the CGADR will be used to measure the subject's readiness for discharge based on parameters including sedation, blood pressure, and adverse events.

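### The SAP's cystitis special-interest list omits bladder pain, which the protocol names for monitoring (minor)

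*SAP*

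**What the plan says.** Protocol 3.2.5, in its paragraph on the risk of treatment-emergent cystitis, says that "subjects will be monitored for adverse events of cystitis, bladder pain, and interstitial cystitis during the study". Protocol 1.1.2.3, in background on chronic ketamine use, gives the usual symptoms of ketamine-induced ulcerative cystitis as "frequency and urgency of urination, dysuria, urge incontinence, and occasionally painful hematuria".

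SAP 6.1 sorts special-interest events into 14 categories, each defined by preferred terms in parentheses. The cystitis entry reads "cystitis (Allergic cystitis, Chemical cystitis, Cystitis, Cystitis erosive, Cystitis haemorrhagic, Cystitis interstitial, Cystitis noninfective, Cystitis ulcerative, Cystitis-like symptom, Pollakiuria, Dysuria, Micturition urgency, Nocturia". The renal category is longer. Part of it reads "Bladder discomfort, Bladder irritation, Bladder outlet obstruction, Cystitis noninfective, Dysuria, Haematuria, Hypertonic bladder, Lower urinary tract symptoms, Micturition urgency, Nephrolithiasis, Nocturia, Pollakiuria", and it later includes Urge incontinence.

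SAP 6.1 also tabulates all treatment-emergent events by system organ class and preferred term, and lists deaths, other serious events and discontinuations due to adverse events.

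The persistent-dissociation category has a label setting a limit of 2 hours from dosing and a single term: "post esketamine administration (dissociation".

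**The concern.** Treatment-emergent events of special interest are part of the primary objective. Amendment 3 gave long-term data on urinary symptoms (cystitis) as one reason for extending the study, so the cystitis incidence is one of the results a reader will look for.

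The SAP list turns the protocol's monitoring commitment into a count. If it leaves out an event that the protocol names in the same breath as two that it includes, the category reports something narrower than was promised. The overall tables do not repair this. Preferred-term rows cannot be added to give the number of subjects with at least one event, because a subject with two terms would be counted twice.

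**Working it through.** No figure in the plan bears on this point. The check compares the protocol's named events with the SAP 6.1 lists.

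**List sizes.** Cystitis has 13 terms and renal disorders 35. Six are shared: Cystitis, Cystitis noninfective, Dysuria, Micturition urgency, Nocturia and Pollakiuria.

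**Where each named event sits** (frequency is matched to Pollakiuria, urgency to Micturition urgency):

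| Event | Protocol source | Cystitis list | Renal list |
|---|---|---|---|
| Cystitis | 3.2.5 | yes | yes |
| Interstitial cystitis | 3.2.5 | yes | no |
| Bladder pain | 3.2.5 | **no** | **no** |
| Frequency | 1.1.2.3 | yes | yes |
| Urgency | 1.1.2.3 | yes | yes |
| Dysuria | 1.1.2.3 | yes | yes |
| Urge incontinence | 1.1.2.3 | no | yes |
| Haematuria | 1.1.2.3 | no | yes |

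Of 8 named events, 5 are in the cystitis list, 2 are under renal disorders only, and 1, bladder pain, is in neither. Bladder pain is not in the other 12 categories either.

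**Could the omission be a wish for specificity?** This is unlikely. Four of the 13 cystitis terms (Pollakiuria, Dysuria, Micturition urgency, Nocturia) are general urinary symptoms, so the list already goes beyond diagnoses of cystitis.

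**Effect on the count.** Let A be the subjects with at least one of the 13 terms and B the subjects with bladder pain. Adding the term changes the category count by

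|A ∪ B| − |A| = number of subjects in B but not in A.

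This lies between 0 and |B|. The omission can only lower the cystitis count or leave it unchanged. The documents give no value for |B| or for its overlap with A, so no estimate is possible.

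**After the change.** Cystitis goes from 13 to 15 terms (Bladder pain and Urge incontinence added). Renal stays at 35, and the shared terms go from 6 to 7, because Urge incontinence is then in both.

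**The case against.** The case for leaving the list alone has substance.

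- **Nothing is lost.** Every treatment-emergent event is tabulated by preferred term. Protocol 3.2.5 discontinues subjects whose cystitis is considered associated with esketamine, so those cases also reach the discontinuation listing. This stands, and it limits the consequence.
- **Diagnoses come first.** Protocol 12.3.1 asks sites to report a diagnosis where signs and symptoms share a cause. Bladder pain within a diagnosed cystitis should be recorded as cystitis and counted. This stands too. What is left is bladder pain without a diagnosis or another listed symptom.
- **Coding is not visible.** The preferred term given to a report of bladder pain depends on the MedDRA version. If it were coded as Bladder discomfort or Bladder irritation, it would be counted under renal disorders, but still not under cystitis.
- **The study is descriptive.** It has a single arm and no hypothesis, so no test result is at risk.

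Some stronger readings are tempting, but the documents do not support them.

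- A reader might infer that the SAP breaks a protocol commitment on urge incontinence as well. It does not. That symptom appears only in background text, largely on near-daily recreational users, and it is counted under renal disorders. What remains is uneven treatment of symptoms from one sentence, and haematuria is in the same position.
- A reader might infer that Dissociative disorder must be added to persistent dissociation, because Phase 2 reported it separately from dissociation and the concomitant-medication summary is also confined to one term: "taking concomitant medication for dissociation events (preferred term of Dissociation". But the term is counted under drug abuse, dependence and withdrawal, and the one case that Protocol 1.1.2.3 describes resolved the same day. Nothing shows that it persists.
- A reader might infer that imputed onset times in SAP 2.6 create false persistent episodes. They cannot, because the label's clock runs from drug administration, not from event onset. Nor does the SAP say that imputed resolution dates feed this category.

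**Conclusion.** The point holds for bladder pain, as a minor one. The protocol names it for monitoring next to two events that the SAP list includes, and it is in 0 of 14 special-interest categories. The cystitis incidence will miss any subject whose only relevant event is coded to that term. The direction of this omission is known (downward or none), but its size is not.

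The conclusion rests on three assumptions: that the lists are exhaustive, which is inferred because they carry no open-ended wording; that the category row counts subjects with at least one listed term; and that bladder pain keeps its own preferred term when coded.

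Urge incontinence is a matter of consistency, with weaker support. The 2-hour limit for persistent dissociation is already stated in the label; only the programming detail is missing.

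**What to change.** Amend the cystitis entry in SAP 6.1:

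1. Add bladder pain, as coded in the MedDRA version used.
2. For consistency, add Urge incontinence and keep it under renal disorders as well.
3. Show the present 13-term list as a sub-row, so that the effect of the change is visible.
4. Show Haematuria as a sensitivity row.

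Optional clarification for persistent dissociation: count only episodes whose recorded end time is more than 2 hours after the first spray, which the protocol's Time and Events notes define as time 0. Show episodes without a recorded end time on a separate row. Dissociative disorder may be shown as a sensitivity row.

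The cost is a text change and a re-run of the special-interest tables, with no new data. The downside is a slightly less specific cystitis category and a slightly higher reported incidence, which the sub-row makes plain.
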